Study 2: Our clinical study is a longitudinal randomized (6 month) cross over controlled clinical trial (RCT) intervention with two parallel arms (ratio: 1:1) with care-as-usual plus care coordination intervention. The purpose of Phase-II clinical trial is to examine effectiveness of the Care4AD platform to improve care coordination and caregivers burden and stress. For the purpose of this study, we will recruit 100 men and women older adults (Age 18+) persons with mild or moderate dementia/memory loss. Including self-reported memory loss and MOCA score of 26 or lower.

Both groups will receive identical Care4AD platform (tablet). However, all feedbacks (e.g., reminder about completed/incomplete tasks) will be activated in the intervention group (IG) and the caregiver will have companion app downloaded on their smartphone. Reminder notifications will be de-activated in the control group (CG) and no app will be supplied. CG will receive conventional care coordination intervention through bi-weekly interview and will be provided with

7/25/24, 1:58 PM Human Protocol Report
scheduled care tasks similar to IG. Participants will be informed that the purpose of this program is to examine effectiveness of a care coordination program to reduce stress and burden of care givers and improve adherence to scheduled care tasks and improve mobility. The type of intervention will not be disclosed to participants at baseline (blinded study design) as both groups will receive some sort of care coordination intervention. In addition, the person who will analyze the data will be blinded to the type of intervention. At the 3 month visit, participants will be crossed over to either intervention or control and follow procedures.

Inclusion Criteria:

Male and female older patients (> 18 years old) with mild or moderate memory loss, self- reported memory loss, or MOCA score 26 or lower, and who are ambulatory and are in a residential home with a caregiver/informant or in a nursing home.

Caregivers and Health Professionals will be included in the subject population.

Exclusion Criteria:

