At the 3 month visit, the following procedures will be completed: Questionnaires, Gait, Balance, Motor-Cognitive Exercise program, Spontaneous physical activity monitoring, Upper Extremity Test, Photos and Media. Crossover will also happen, intervention group will become controls and controls will become part of the intervention group.

At 6 months, the following procedures will be completed: Questionnaires, Gait, Balance, Spontaneous physical activity monitoring, Upper Extremity Test, Photos and Media. At the end of the visit, the subject will return the platform to the research team.

Section G: Sample Size/Data Analysis

G1. Sample Size

How many subjects (or specimens, or charts) will be used in this study?

Local: 130 Worldwide: 130

Please indicate why you chose the sample size proposed:

Phase I: N=30 total subjects including 10 eligible Individuals With Dementia, at least one of the caregivers (n=10), and 10 expert clinicians unaffiliated with this project, who are providing care for Individuals With Dementia and their caregivers. The sample size for Phase I is chosen based on our experience with assessing technologies for older populations and also considering the timeline and budget limitation for Phase I. Over the past decade, we have evaluated the usability of a number of such technologies and we have found that the proposed sample size is adequate for identifying potential shortcomings that might require design or implementation modifications.

Phase II: N=100 total subjects, Individuals With care-givers, age 18+, who are supporting an individual with memory loss, aged 50+, male and female, who satisfied inclusion and exclusion criteria described in the following. The required sample size for Phase II was calculated based on our primary endpoints: 1) reduce burden for the caregivers in the Intervention group, 2) better adherence in the Intervention group compared to control group, and 3) change in functional performance over 6 month.

G2. Data Analysis

Provide a description of your plan for data analysis. State the types of comparisons you plan (e.g. comparison of means, comparison of proportions, regressions, analysis of variance). Which is the PRIMARY comparison/analysis? How will the analyses proposed relate to the primary purposes of your study?

7/25/24, 1:58 PM Human Protocol Report

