Study 2: Results of the user experience questionnaires will be calculated as median (range) for each Likert-scale question. Unpaired t-tests, Mann-Whitney u-tests, and Chi-square will be used for baseline between groups comparison to verify effectiveness of randomization. Linear mixed models will be used to test the effect of the Care4AD care coordination intervention on caregiver burden/stress at 6 months compared to baseline and between groups. Mixed models that accommodate the longitudinal design, allow for testing differences between groups in patterns over time, as well as at specific time points are consistent with an intention to treat analysis, and are valid for data which are missing at random. Appropriate mixed models (linear for continuous or Generalized Estimating Equations (GEEs) for non-continuous or non-parametric variables) will be used to test the intervention effect for each of the secondary outcomes (depression, cognitive function, QoL, fear of falls, neurotic tendency including fatigue, physical activity, adverse events, missing appointments). Univariate linear regression analyses will be performed to delineate predictive factors of training response for the primary study endpoint (pre- to post- changes in care coordination outcomes). Baseline values include age, gender, BMI, fear of falling, ADL-status, comorbidity, cognitive performance, depression, stage of AD, and baseline motor variables (e.g., balance and gait speed). We will use Spearman correlation coefficient to compare changes in quantitative metrics of exercise performance over the course of the program with in clinic assessments of functional performance (e.g., gait speed) and cognitive performance (e.g., MoCA). We will assess the agreement between Care4AD derived ADL, the Katz Index, and the Lawton-ADL. To demonstrate the acceptability of Care4AD application, we will use TAM model described above using 5-point Likert response questions. For all assessments, a p-value of 0.050 or less will be considered as statistically significant level. To evaluate the effect of sex as biological variable, we will examine whether acceptability and benefits of Care4AD platform to improve care coordination outcomes (between groups as well as compared to baseline) are different between men and women.

Section H: Potential Risks/Discomforts

H1. Potential Risks/Discomforts

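### The only dated caregiver-burden contrast is at 6 months, after the arms swap at 3 months: with equal effects it is wrong-signed or null by randomised arm, and diluted by carryover by condition in force

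*Combined protocol and SAP*

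**What the plan says.** - **Design.** Section F1 (Study 2) describes a 6-month randomised crossover, 1:1, and also calls it two parallel arms. It states: "At the 3 month visit, participants will be crossed over to either intervention or control and follow procedures". Section F2, under the 3-month visit, says: "Crossover will also happen, intervention group will become controls and controls will become part of the intervention group". No washout is described.
- **Meaning of group.** F1 separates the groups by what they receive. For controls: "Reminder notifications will be de-activated in the control group (CG) and no app will be supplied".
- **Endpoint.** G1 lists reduced caregiver burden in the intervention group as the first primary endpoint, without a time point.
- **Analysis.** G2 gives one burden contrast with a date. Linear mixed models will "test the effect of the Care4AD care coordination intervention on caregiver burden/stress at 6 months compared to baseline and between groups". The next sentence says, in general terms, that such models can test "differences between groups in patterns over time, as well as at specific time points are consistent with an intention to treat analysis". G2 later describes the primary endpoint as pre-to-post change in care coordination outcomes. Its analysis by sex also uses between-group and versus-baseline comparisons.
- **Not stated.** G2 names no 3-month contrast, condition effect, period or sequence term, or carryover assumption.
- **Data.** The Zarit Burden Interview is named under Questionnaires in the F2 baseline list. F2 repeats Questionnaires at 3 and 6 months.

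**The concern.** The comparison is dated three months after each arm has taken on the other's condition. Group can then mean the arm to which a participant was randomised or the condition now in force. F1 and F2 lean towards the second, and G2's appeal to intention to treat leans towards the first. At 6 months the two meanings give estimates of opposite sign from the same data.

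Comparing 6 months with baseline does not help. By then every participant has had three months of each condition, so the change combines treatment, carryover and time trend with no concurrent control. The pre-to-post wording has the same defect.

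A platform that works could therefore appear ineffective or harmful on a primary endpoint, while the clean randomised comparison at 3 months has no designated role.

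**Working it through.** **Inputs from the documents.** Swap at 3 months (F1, F2); visits at baseline, 3 and 6 months (F2); N = 100 (G1) at 1:1 (F1), so 50 per arm; significance level 0.05 (G2), taken as two-sided.

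**The plan's own figure.** N = 100 cannot be reproduced, because G1 gives no effect size, SD, power or dropout. Working backwards with the normal formula, 50 per arm detects (1.960 + 0.842) × √(2/50) = 0.56 SD at 80% power and 0.65 SD at 90%.

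**Assumed inputs.** Effect d = 0.3 or 0.5 SD; within-person correlation r = 0.5 to 0.7; carryover L from 0 to 1; 50 per arm, or 40 after 20% loss. The documents give none of these. Some persistence is plausible, since both arms keep a tablet and a task schedule.

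**Expected differences.** Let d1 and d2 be the burden reductions in periods 1 and 2, and take Care4AD-first minus control-first (negative favours Care4AD-first). A period effect common to both arms cancels.

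- Month 3: -d1.
- Month 6, by randomised arm: -L·d1 + d2. The sign is wrong whenever d2 > L·d1. With equal effects this is +d(1-L).
- Month 6, by condition in force, equal effects: -d(1-L).
- Both periods by condition, equal effects: (month-3 minus month-6 difference)/2 = [-d - d(1-L)]/2 = -d(1-L/2).

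Simulated mixed models with a true effect of -0.57 SD and 50 per arm (60 replicates at each L) agree:

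| L | 3 months, by arm | 6 months, by arm | Both periods, by condition |
|---|---|---|---|
| 0 | -0.58 | +0.58 | -0.58 |
| 0.5 | -0.56 | +0.30 | -0.43 |
| 1 | -0.53 | +0.02 | -0.28 |

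**Variances** (SD 1, n per arm, compound symmetry): unadjusted 2/n; change score 4(1-r)/n; ANCOVA 2(1-r²)/n; two-period (1-r)/n. Power is from the noncentral t.

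**Chance of a significant wrong-direction result at 6 months by randomised arm** (range over the unadjusted, change-score and ANCOVA tests, r = 0.5 to 0.7):

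| L | d=0.5, 50/arm | d=0.3, 50/arm | d=0.5, 40/arm | d=0.3, 40/arm |
|---|---|---|---|---|
| 0 | 70-93% | 32-55% | 60-87% | 26-46% |
| 0.25 | 46-74% | 20-34% | 38-64% | 17-29% |
| 0.5 | 24-41% | 11-18% | 20-34% | 10-15% |
| 0.75 | 9-14% | 6-8% | 8-12% | 5-7% |
| 1 | 2.5% | 2.5% | 2.5% | 2.5% |

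**Power at 6 months by condition in force** (ANCOVA, d = 0.5, 50 per arm): 82-93%, 57-74%, 30-41%, 11-14% and 2.5% at the same five values of L. The 3-month ANCOVA has 82-93% at every L.

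**The case against.** The strongest reply is that F2 does state membership after the swap and F1 defines the groups by what is switched on. On that wording, between groups after month 3 means condition in force, and the sign is right. Intention to treat in a crossover is compatible with analysing each period by its assigned condition. A mixed model fitted that way to all visits would give -d(1-L/2), the same expectation as the fix proposed here. The G2 sentence can also be parsed as two separate comparisons, with the 6-month date attached only to the change from baseline. The wrong sign needs d2 > L·d1: if the period-2 effect were half the period-1 effect and L were 0.6, the sign would be right. A reader who remembers the swap would not infer harm. The study is categorised as a pilot, and the analyst is blinded.

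Much of this is fair, and it makes condition in force the more natural reading. It does not rescue the plan. G2 never says that group is condition in force or that both periods enter the estimate. The stated 6-month contrast is diluted even on the favourable reading. The general remark about time points describes what a model can do and designates no test. Blinding limits a data-driven choice of reading but does not say which contrast is run. F1 gives the purpose of the study as examining effectiveness, and G1 says N was calculated from primary endpoints, so the pilot label does not excuse the gap.

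If N = 100 counted patients and caregivers together, there would be 25 dyads per arm and the percentages above would be lower. F1's 100 persons with memory loss supports 50, and the signs do not depend on it.

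**Conclusion.** The concern holds, and the plan must be corrected. Followed as written, the dated burden contrast is wrong-signed or null by randomised arm, diluted by condition in force, or an uncontrolled change that mixes both conditions. With equal effects in the two periods, the two between-group readings give +d(1-L) and -d(1-L). That result is algebra and needs no undocumented figure.

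The size of the problem does rest on assumed d, r, L and numbers per arm. Over the values examined, the chance of a significant wrong-direction result by randomised arm runs from 2.5% with complete carryover to 93% with none. The data for a valid comparison are already scheduled; the plan does not say that they will be used for one.

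**What to change.** **In G2:**

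1. Replace the 6-month between-group contrast with the Care4AD condition effect from a mixed model of the 3- and 6-month burden scores. Use condition, period and sequence as fixed effects and a participant random effect. State that it assumes no carryover and is biased towards the null, to -d(1-L/2), if carryover exists.
2. Report the baseline-adjusted difference between randomised arms at 3 months, with questionnaires completed before the switch, as the carryover-free supportive analysis. If the sponsor expects material carryover, make this primary instead.
3. Fix the choice before any data by group are seen, and do not base it on a carryover test in the trial data.
4. Define group as randomised sequence or condition in force wherever it appears, including the analysis by sex. Define the 6-month change in functional performance (G1, third primary endpoint) in the same way.
5. State that the Zarit Burden Interview is among the questionnaires at 3 and 6 months.

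**Cost.** This is mainly wording, with one line each for the Zarit and for completing questionnaires before the switch. No visit or participant is added.

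**Trade-off** (d = 0.3 SD, r = 0.5, assumed):

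| L | Two-period power, 50/arm | Two-period power, 40/arm |
|---|---|---|
| 0 | 84% | 76% |
| 0.25 | 74% | 64% |
| 0.5 | 61% | 51% |
| 0.75 | 46% | 38% |
| 1 | 32% | 26% |

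The 3-month ANCOVA has 40% (50 per arm) or 33% (40 per arm) at every L. Under these variance formulas, power is equal at L = 2(1 - 1/√(2(1+r))), about 0.85 at r = 0.5 and 0.92 at r = 0.7, whatever d and n. Below that the two-period model has more power, but carryover biases its estimate. Its mean squared error becomes the larger one above L = (2/d)·√((1-r)(1+2r)/n). With 50 per arm and r = 0.5 to 0.7, that threshold is 0.57 to 0.48 at d = 0.5 and 0.94 to 0.80 at d = 0.3.

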At the baseline visit, we will perform the following measurements.

Medical History: We will record socio-demographics (e.g. age, gender, BMI, education, marital status, etc) and medical history (health status including comorbidities, history of falls, history of hospitalization, prior surgery, duration of diagnosed as MCI, co-existing medical conditions, hearing and visual performance, frailty status, etc), medication use, etc.

Questionnaires: We will ask the subject to answer a series of health related questionnaires such as quality of life (Promise Global), demographics, anxiety (Beck Anxiety Scale), instrumental daily living activities (Lawton-IADL), Pain-Mobility, fear of falling (FES-I), frailty (Fried Frailty), MOCA, MMSE or Trail Making A&B for cognitive status, and depression (GSD). Their caregivers will also be asked to complete the Zarit Burden Interview, a validated survey for dementia caregivers. These questionnaires will be completed through RedCap.

Phone calls: Research Coordinators will call subjects to ask health-related questions. They may also call the subject for study related questions.

Gait: Gait will be assessed using LEGSys, a validated body-worn sensor system. LEGSys uses five inertial measurement units attached to right and left anterior shins, right and left anterior thighs, and posteriorly to the lower back. LEGSys uses a two-link inverted pendulum model based on the subjects height to determine spatiotemporal gait parameters such as stride velocity, stride length, stride time, double support, single support, and stride-to-stride variability, and gait initiation. In addition, COM range of motion during walking will be calculated based on the data from the sensor attached to the lower back. Gait will be assessed under 2 conditions; walking at a habitual speed and walking at maximum speed. In addition,

Balance: Balance will be quantified using BalanSens, a validated body-worn sensor system. BalanSens measures ankle and hip motion in three dimensions, COM sway, and coordination between ankle and hip motion. Subjects will be asked to stand in different positions such as feet together and feet in semi-tandem with two conditions: eyes open and eyes closed.

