Spontaneous daily physical activity monitoring : Daily mobility performance and inactivity will be objectively monitored using a validated wearable technology named PAMSys, a sensor that can be worn as a pendant around the neck. We will assess multiple parameters such as number of taken steps, longest walking bout, standing duration, sedentary behavior, etc. Subjects will be monitored for up to 1 week continuously at baseline and at the end of the study. Subjects will be provided with a prepaid fedex envelop to return the Pamsys device to the research team.

Upper Extremity Test: Investigators will measure arm motion from each participant by implementing a validated technology based on wearable sensor system named LegSys. This system will assess respectively spatio-temporal parameters of arm motion as well as gait in a clinical setting. The LegSys system will be used with one sensor to capture arm motion, the sensor will be placed at the subject's wrist. While being at a comfortable position, the subject will be asked to flex and extend their arm for 20 seconds at a fast speed. Subject will also be asked to repeat this task but counting backwards as they flex and extend their arm (dual task).

Photos and media: We will be asking permission of the subject to take photos, film videos and/or record audio during the visits.

Care4AD: The research coordinator will provide the platform and explain to the subject and their caregiver how to interact with it. Together they will set up a schedule of regular IADL to follow. Intervention group will receive reminder notifications on their tablet to complete tasks and caregivers will be able to edit tasks on companion app downloaded on their smartphone. Control group will not receive reminder notifications and caregiver companion app will not be given.

Phone calls: Research Coordinators will call subjects bi-weekly to assess compliance to IADL schedule set up on the Care4AD platform. During the phone call, the coordinator will ask questions regarding acceptability and perceived usefulness and benefit of the platform. They may also call the subject for study related questions and to assess of there have been no adverse events (falls, hospitalization, etc).

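### The caregiver-burden model does not say how the baseline Zarit score enters, so precision available from data already collected is not secured

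*Combined protocol and SAP*

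**What the plan says.** The burden analysis in G2 (Study 2) is a linear mixed model for the effect of the intervention on "caregiver burden/stress at 6 months compared to baseline and between groups". The text says that mixed models suit longitudinal data, fit an intention-to-treat analysis and are valid when data are missing at random. It lists no fixed effects, no covariates, no constraint on baseline means and no period or sequence term. The only list of baseline variables in G2 belongs to the univariate regressions for predictors of response, and baseline burden is not on it.

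The data needed for adjustment exist. F2 says of the baseline visit: "Their caregivers will also be asked to complete the Zarit Burden Interview, a validated survey for dementia caregivers". Questionnaires are repeated at 3 and 6 months.

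The groups swap at 3 months. F1 says "At the 3 month visit, participants will be crossed over to either intervention or control and follow procedures", and F2 says "Crossover will also happen, intervention group will become controls and controls will become part of the intervention group".

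G1 lists lower caregiver burden first among three primary endpoints. It says that the Phase II sample size of 100 was calculated from those endpoints, but shows no effect size, standard deviation, power or correlation.

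**The concern.** A mixed model does not adjust for baseline by itself. What matters is how baseline enters. If it is one of the repeated outcomes and each group has its own baseline mean, the group-by-time contrast on complete data is the difference between groups in mean change. Under randomisation the two groups share a baseline mean in expectation, and a model that uses this (by constraint or by covariate) gives a smaller standard error for the same effect.

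The G2 wording, which compares with baseline and between groups, reads most naturally as the unconstrained version. G1 states no power margin, so nothing in the documents shows that the trial can absorb the lost precision on its first-listed primary endpoint.

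**Working it through.** **Plan's own figure.** The 100 in G1 cannot be reproduced, because none of its inputs is given.

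**Inputs.** Allocation is 1:1 (F1). Alpha is 0.05 (G2), taken as two-sided because the side is not stated. The correlation r between Zarit scores at two visits is an assumption, 0.3 to 0.8. Complete data and unit SD are assumed. The number of caregivers is unclear: F1 counts 100 persons with memory loss, while G1 words its 100 around caregivers. The variance ratios do not depend on it; the standard errors and power below assume 50 per group.

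Write d0, d3, d6 for the differences between the two randomised sequences at baseline, 3 and 6 months.

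**1. The 6-month contrast as written**
- Separate baseline means: the estimate is d6 − d0, with variance factor 2(1−r).
- Common baseline mean or covariate: the estimate is d6 − r·d0, with variance factor 1−r².
- Ratio: (1−r²) / (2(1−r)) = (1+r)/2.
- SE at n = 50 per group: √((2/50) × factor).

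| r | 2(1−r) | 1−r² | ratio | SE, change score | SE, adjusted | 100/ratio |
|---|---|---|---|---|---|---|
| 0.3 | 1.40 | 0.91 | 0.65 | 0.237 SD | 0.191 SD | 154 |
| 0.5 | 1.00 | 0.75 | 0.75 | 0.200 SD | 0.173 SD | 133 |
| 0.7 | 0.60 | 0.51 | 0.85 | 0.155 SD | 0.143 SD | 118 |
| 0.8 | 0.40 | 0.36 | 0.90 | 0.126 SD | 0.120 SD | 111 |

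The last column is the number of caregivers analysed by change score that matches 100 analysed with adjustment. For an assumed effect of 0.5 SD at r = 0.5, power rises from 70.5% to 82.3%. A simulation of 20,000 trials at r = 0.5 and 50 per group gave a covariate-to-change variance ratio of 0.758, with both mean estimates about zero. That agrees with 0.75 plus about 1% for estimating the slope.

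**2. First-period contrast, or a crossover model with carryover**
- First period: the same algebra with d3 in place of d6, so the ratio is (1+r)/2 with r the baseline-to-3-month correlation.
- With a carryover term λ at 6 months, the means are (0, τ, −τ+λ) against (b, b+τ, b−τ+λ). The free λ absorbs d6, so τ is again estimated from d3 and d0. The ratio is (1+r)/2 under compound symmetry and under AR(1).

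**3. Period-coded crossover without carryover, by generalised least squares**

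The common-baseline model has means (0, τ, −τ). The comparator keeps baseline as a repeated outcome with a sequence offset, (b, b+τ, b−τ).
- Compound symmetry: the offset is orthogonal to τ, so the ratio is 1.000 and the gain is 0%.
- AR(1), with r between adjacent visits: ratio = 1 − r²(1−r) / ((3−r)(2+2r+r²)).
  - r = 0.3: 1 − 0.063/7.263 = 0.991
  - r = 0.5: 1 − 0.125/8.125 = 0.985
  - r = 0.7: 1 − 0.147/8.947 = 0.984
- The gain is therefore about 1% to 2%.

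Against a model that leaves baseline out altogether, the AR(1) ratio is 2(1+r)/(2+2r+r²) = 0.967, 0.923 and 0.874 at r = 0.3, 0.5 and 0.7. That comparator fits G2 poorly, since G2 does compare with baseline.

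**The case against.** The strongest objection is that the large gain belongs to a contrast that should not survive. By 6 months both sequences have had both conditions, so a between-group difference then does not isolate the platform's effect, and a smaller standard error on it is worth little. This stands. A reader might infer that baseline adjustment rescues the 6-month comparison, but it does not; how the crossover is to be analysed must be settled first. If the answer is a period-coded model without carryover, the gain nearly vanishes. The full gain returns with a first-period or carryover-term analysis. G2 names neither, though the documents describe no washout and both remain possible.

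Second, G2 is silent rather than wrong. A reader might infer that the plan has chosen a change-score analysis, pointing to "pre- to post- changes in care coordination outcomes" in the same section. The documents do not support that: the phrase describes the outcome of the predictor regressions, not the burden model. A longitudinal mixed model that includes baseline is compatible with a common baseline mean, and if that is intended nothing is lost.

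Third, both estimators are valid and the study is classified as a pilot, so this may look like preference. That is fair as to seriousness. It does not remove the reason to specify, because the better option uses data already collected and, on complete data, the common-mean version is never less precise in the cases worked.

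Fourth, r is assumed, and the saving shrinks as r rises: 10% at 0.8, and 5% at 0.9, where (1+0.9)/2 = 0.95. This also stands.

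**Conclusion.** The point holds as a conditional gain in efficiency. G2 specifies no baseline Zarit covariate and no common baseline mean. If separate group baseline means are fitted, the between-group contrast has a variance 1/0.90 = 1.11 to 1/0.65 = 1.54 times that of the adjusted one, for assumed r from 0.8 down to 0.3. This covers the 6-month contrast as written, a first-period contrast and a crossover model with carryover. For a period-coded crossover without carryover that keeps baseline as a repeated outcome, the loss is 0% under compound symmetry and about 1% to 2% under AR(1). If a common baseline mean is already intended, there is no loss.

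A reader might infer that the burden result would be biased, or its type I error inflated, without adjustment. Neither follows: over randomisations the change-score contrast is unbiased. Nor do the documents support a fixed percentage loss, since they give neither r nor the crossover model. The figures rest on complete data, equal variances across visits, and a baseline score unaffected by allocation.

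**What to change.** When the burden model in G2 is written to reflect the 3-month crossover, add that the two randomised sequences are constrained to a common baseline Zarit mean, or that baseline Zarit is a covariate. The common-mean version keeps caregivers whose baseline score is missing. The covariate version drops them unless this is handled, and estimating its slope costs about 1% of variance at 50 per group.

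State in F2 that the baseline Zarit is completed before the platform is handed out or allocation is disclosed. Questionnaires go through REDCap and enrolment may be remote, and nothing now fixes that order; the common-mean constraint depends on it.

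Do the same for continuous secondary outcomes with a true pre-intervention baseline, subject to three checks:
- **Physical activity:** F2 says "Subjects will be monitored for up to 1 week continuously at baseline and at the end of the study". The baseline week may run after the platform is handed out, and it qualifies only if it ends before reminders start.
- **Cognitive function:** F2 lists alternatives, "MOCA, MMSE or Trail Making A&B for cognitive status". One instrument must be collected for everyone.
- **Adverse events, missed appointments and adherence** during the study have no such baseline and are left out.

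The cost is a few sentences in G2 and F2 and no new assessment, although the order of baseline procedures must be controlled. The 6-month contrast needs its own correction.

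### GEE is grouped with the mixed models that the plan calls valid under missing at random; ordinary GEE lacks that property, so dropout could bias the non-continuous secondary outcomes

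*Combined protocol and SAP*

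**What the plan says.** Section G2 (Study 2) assigns caregiver burden to a linear mixed model: "Linear mixed models will be used to test the effect of the Care4AD care coordination intervention on caregiver burden/stress at 6 months". It then says that mixed models "are consistent with an intention to treat analysis, and are valid for data which are missing at random". The following sentence turns to the secondary outcomes: "Appropriate mixed models (linear for continuous or Generalized Estimating Equations (GEEs) for non-continuous or non-parametric variables) will be used to test the intervention effect". Those outcomes are listed as "depression, cognitive function, QoL, fear of falls, neurotic tendency including fatigue, physical activity, adverse events, missing appointments".

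The plan does not say which of them go to the linear model and which to GEE. By type, adverse events and missed appointments are the clear GEE candidates. The missing-at-random sentence is the plan's only provision for missing data. G2 gives no working correlation, weighting, imputation, likelihood-based alternative for non-continuous outcomes or missing-data sensitivity analysis. No dropout rate is given anywhere.

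**The concern.** The missing-at-random property belongs to models fitted by likelihood. GEE is a marginal moment method and not a mixed model. Without weights it is in general consistent only under missing completely at random, or when missingness depends only on modelled covariates such as arm. Calling it a mixed model straight after the validity statement invites the reader to extend the property to it.

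This matters here because there are three visits over 6 months (section F2), so participants can leave after an outcome has been recorded, and section H1 lets them leave at any time. The arms also experience different things: reminders and a companion app in one, neither in the other. Dropout that depends on earlier outcomes and differs by arm is plausible, though the documents do not show it. If it occurred, a biased secondary result could be reported as protected against dropout.

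**Working it through.** **No plan figure to reproduce.** The question concerns a property of an estimator. G1 gives "Phase II: N=100 total subjects" without an effect size, SD, power or dropout rate.

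**Step 1: mechanism.** With an independence working correlation and a saturated condition-by-visit model, GEE returns the mean of those still observed. Let *p* be the event rate, *d*₁ and *d*₀ the dropout probabilities after a month-3 event and non-event, and *q*₁ and *q*₀ the month-6 event probabilities given a month-3 event or not.

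- Share of the retained who had a month-3 event: *s* = *p*(1−*d*₁) / [*p*(1−*d*₁) + (1−*p*)(1−*d*₀)]
- Observed month-6 mean: *m* = *s*·*q*₁ + (1−*s*)·*q*₀
- Bias within an arm: (*s*−*p*)(*q*₁−*q*₀). It cancels between arms under no effect only if *s* is the same in both.

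**Step 2: inputs, all assumed.** Binary outcome, no effect, *p* = 0.45, random intercept with SD 2 on the logit scale. Dropout between months 3 and 6 after an event is 50% in the arm starting as control and 20% in the arm starting on the intervention; it is 5% otherwise. Overall dropout is 0.05 + 0.45×0.45 = 25% and 0.05 + 0.15×0.45 = 12%. Integrating over the random intercept gives *q*₁ = 0.666 and *q*₀ = 0.273 (check: 0.45×0.666 + 0.55×0.273 = 0.45).

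**Step 3: month-6 means by starting arm.**

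- Starting as control: *s* = 0.225/(0.225+0.5225) = 0.301; *m* = 0.301×0.666 + 0.699×0.273 = 0.391
- Starting on intervention: *s* = 0.36/(0.36+0.5225) = 0.408; *m* = 0.408×0.666 + 0.592×0.273 = 0.433
- Difference by starting arm: 0.433 − 0.391 = +0.042, where the truth is 0

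**Step 4: respect the crossover.** Sections F1 and F2 swap the conditions at month 3. Assume no carry-over and dropout that follows the starting arm.

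- Period 1 is complete, so its bias is 0.
- In period 2 the arm that started as control is on the intervention, so intervention minus control is 0.391 − 0.433 = −0.042.
- Pooled over both periods: (0 − 0.042)/2 = **−0.021**
- Exchanging the two arms' dropout rates gives +0.021. Identical rates give 0.

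**Step 5: simulations with the crossover (same assumed dropout rates).**

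| Quantity | Full data | Independence GEE or available-case means |
|---|---|---|
| Pooled risk difference, run 1 | −0.143 | −0.162 (shift −0.019) |
| Pooled risk difference, run 2 | −0.147 | −0.168 (shift −0.021) |
| Condition OR, no effect | 1.00 | 0.92 |
| Condition OR, with effect | 0.543 | 0.495 |

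The risk-difference shifts are 0.019/0.143 = 13% and 0.021/0.147 = 14% of the effect, here exaggerating it. Exchangeable GEE and inverse-probability-weighted GEE stayed within 0.01 of the full-data odds ratios. With identical dropout in both arms and an effect present, the risk difference was −0.149 against −0.148.

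**Step 6: a second set of assumed inputs, for mechanism only.** Three visits, 40% event rate, no effect, latent correlation 0.5 or 0.8, arms held fixed to month 6. The month-6 risk difference from independence GEE, in percentage points, was:

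| Dropout per visit (no prior event / prior event) | Corr. 0.5 | Corr. 0.8 |
|---|---|---|
| Completely at random, 15% | +0.3 | +0.2 |
| Same in both arms, 5%/25% | about 0 | about 0 |
| Control 5%/25%, intervention 13%/13% | +3.3 | +5.9 |
| Control 5%/25%, intervention 20%/5% | +6.7 | +12.0 |

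Exchangeable GEE stayed within about 1 point of zero throughout, including when the true correlation was autoregressive. Weighting brought the last row to +0.4 and +0.8. At n = 100, rejection at 0.05 with independence GEE was 4.5–8.7% in the third row and 7.5–15.8% in the fourth, against 3.3–5.5% with exchangeable. These sizes ignore the crossover and do not transfer to this trial.

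**The case against.** **No sentence says that GEE is valid under missing at random.** This is right. The statement's subject is mixed models, and it follows the linear model for burden. It reaches GEE through the label and its position. A reader might infer that the plan asserts the property of GEE outright; the text does not go that far. The label is still wrong, though, and nothing else in the plan covers missing data for these outcomes.

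**The bias needs several conditions together.** It needs a working correlation at or near independence, dropout driven by earlier outcomes, and a pattern that differs by arm. The documents state none of these. This stands: the bias is possible, not predicted.

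**A large loss of effect does not carry over.** With arms held fixed to month 6 and the Step 2 dropout rates, a true odds ratio of 0.52 appears as 0.61, and the risk difference falls from −0.153 to −0.110. A reader might infer that over a quarter of the effect would be lost. The crossover in F1 and F2 rules that reading out: the conditions have been exchanged by then, the pooled shift is about half the size, and its sign can reverse. G2 does not describe a crossover analysis. If it is read literally as a month-6 comparison of starting arms, that contrast moves by 0.042, but it is not intervention minus control with the original labels.

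**The scope is narrow.** F1 classes the study as a pilot, and adverse events are also asked about in bi-weekly calls (F2), so their data may not resemble a two-visit binary outcome. Both stand. They limit the weight of the point but do not correct the statement.

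**Conclusion.** The point holds as a correction to the analysis text. The plan places GEE under a property that unweighted GEE does not have in general, and provides nothing that would supply it. The non-continuous secondary outcomes could be biased if dropout depends on earlier outcomes and differs by arm.

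Under the assumed inputs, with the crossover, no carry-over and dropout following the starting arm, independence GEE shifts the pooled risk difference by about 0.02 in either direction. With exchangeable working correlation or identical dropout patterns the shift is about nil. The plan leaves the deciding choice, the working correlation, unstated.

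A reader might also infer that the primary analysis is compromised. The documents do not support that. Caregiver burden has a linear mixed model, to which the statement properly applies. G1 also names adherence and functional performance as primary endpoints, but the GEE sentence covers the listed secondary outcomes and does not assign those two endpoints to GEE.

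**What to change.** In section G2:

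1. Limit the missing-at-random statement to the likelihood-based mixed models, and stop describing GEE as a mixed model.
2. List which secondary outcomes are treated as non-continuous.
3. For those outcomes choose one of:
   - GEE with a stated non-independence working correlation (for example exchangeable), after multiple imputation or with inverse-probability-of-dropout weights;
   - a likelihood-based generalised linear mixed model, with marginal effects reported.

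Merely narrowing the statement and naming a working correlation would correct the text. It would remove most of the bias in the cases simulated, but it gives no general protection under missing at random.

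The cost is wording and modest programming, with no change to visits, data collection or sample size. An imputation or dropout model must be specified, and with 100 participants it may rest on few dropouts. GLMM coefficients are subject-specific unless marginalised.
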